5.1.1.3. Time to Response

Time to response (TTR) is defined as the time from the date of first dose of MIRV until the date of the first observed CR or PR. TTR is only defined for patients who have a confirmed BOR of CR or PR.

5.1.2. PFS

PFS is defined as the time from the date of first dose of MIRV until the date of PD or death from any cause, whichever occurs first. PFS is defined based on radiological assessments and determined by the Investigator. Clinical progression is not considered a progression endpoint.

Table 3 summarizes the rules to be used for PFS. When an analysis cutoff date is implemented, only data (deaths and radiological assessments) occurring on or prior to the cutoff date will be used for analysis.

Situation	Date of PFS ^a Event or Censoring	Outcome
No post-baseline radiological assessments, and patient did not die within 105 days of first dose	Date of first dose	Censored
No post-baseline radiological assessments, and patient died within 105 days of first dose	Date of death	Death
Death	Date of death	Death
Radiological Progression	Date of first radiological assessment indicating progression (ie, OR = PD).	Progression
New anti-cancer therapy prior to PD or death (including palliative radiotherapy during study treatment)	Date of last radiological assessment prior to the start of the new anticancer therapy	Censored
No death or PD	Date of last radiological assessment	Censored
PD or death after missing 2 or more consecutive radiological assessments (PD or death date - last radiological assessment date $+1 \ge 105$ days)	Date of last adequate radiological assessment showing no PD	Censored

Table 3:PFS Definitions

Abbreviations: OR = overall response; PD = disease progression; PFS = progression-free survival.

^a Includes radiographic progression only.

5.1.3. OS

OS is defined as the time from the date of first dose until the date of death from any cause.

Patients who are alive or lost to follow-up at the analysis are censored at the last known date at which they were known to be alive. When an analysis cutoff date is implemented, only deaths occurring on or before the cutoff date are counted as OS events. Patients whose date of death or the last date at which the patient was known to be alive (eg, after the data cutoff date) will be censored at the analysis cutoff date.

5.1.4. GCIG CA-125 Response

A GCIG CA-125 response is defined as $a \ge 50\%$ reduction in CA-125 levels from baseline. The response must be confirmed and maintained for at least 28 days. The CA-125 response will be conducted using the CA-125-Evaluable population. The date of response corresponds to the date when the CA-125 level is first reduced by 50%. The summary table for CA-125 will include the number (percentage) of patients in the CA-125-Evaluable population, and that number will then be used as the denominator for CA-125 response rate.

5.2. Primary Efficacy Outcome Analysis

The primary endpoint of ORR will be calculated based on the Efficacy Evaluable population and its 95% exact CI will be estimated using the Clopper-Pearson method.

5.3. Secondary Efficacy Analyses

5.3.1. Key Secondary Efficacy Analysis

The key secondary endpoint of DOR will be summarized in patients with a confirmed BOR of CR or PR only.

The distribution of DOR will be summarized using the Kaplan-Meier method. DOR rates will be reported at 3-month intervals (eg, 3 months, 6 months, etc.). Median DOR will be estimated from the 50th percentile of the corresponding Kaplan-Meier estimates. 95% CIs for the 3-month intervals and median DOR will also be provided.

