4. INVESTIGATIONAL PLAN

4.1. Study Design

4.1.1. Overview and Schema

This Phase 3 study is designed to evaluate the efficacy and safety of MIRV in patients with platinum-resistant high-grade serous EOC, primary peritoneal, or fallopian tube cancer, whose

tumors express a high level of FR α . Patients will be, in the opinion of the Investigator, appropriate for single-agent- therapy. FR α expression will be defined by the Ventana FOLRI Assay.

Approximately 110 patients who have provided informed consent and meet study entry criteria will be enrolled to achieve a total of 105 efficacy evaluable patients. Efficacy evaluable patients include those who have measurable lesions (per RECIST v1.1) at baseline and received at least 1 dose of MIRV.

Enrolled patients will receive single-agent MIRV at 6 mg/kg AIBW administered Q3W.

Tumor response will be evaluated by the Investigator using RECIST v1.1. CT or MRI scans will be collected for sensitivity analysis by a BICR.

Patients will continue to receive MIRV until PD, unacceptable toxicity, withdrawal of consent, death, or until the Sponsor terminates the study (whichever comes first).

Tumor assessments, including radiological assessment by CT/MRI scan, will be performed at Screening and subsequently every 6 weeks (\pm 1 week) from C1D1 for the first 36 weeks then every 12 weeks (\pm 3 weeks) until PD, death, the start of new anticancer therapy, or patient's withdrawal of consent, whichever occurs first.

Patients who discontinue MIRV for reasons other than progressive disease (PD) will continue with tumor assessments until documentation of PD or the start of a new anticancer therapy, whichever comes first. Prior to Week 36 (from Cycle 1, Day 1), assessments should occur every 6 weeks (\pm 1 week) as allowed by local requirements but must occur at an interval of no more than 12 weeks. After Week 36, assessment will occur every 12 weeks (\pm 3 weeks) until documentation of PD or the start of new anticancer therapy.

All patients who discontinue study drug will be followed every 3 months (\pm 1 month) until death, lost to follow-up, withdrawal of consent for survival follow-up, or EOS, whichever comes first.

There will be no interim analysis.

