10.1. Sample Size

Primary endpoint is confirmed ORR per Investigator assessment.

A sample size of 105 efficacy evaluable patients achieves 91% power to detect a difference in ORR of 12% (24% vs. 12%) using a 1-sided binomial test. The target significance level (1-sided α level) is 0.025. The actual significance level achieved by this test is 0.0242. These results assume that the ORR is 12% under the null hypothesis and 24% under the alternative hypothesis.

Patients who have received at least 1 dose of MIRV but are not efficacy evaluable will be included in Safety Analysis Population. However, these patients will not be included in the Efficacy Evaluable Population and will be replaced for the purpose of sample size determination. A total of approximately 110 patients will be enrolled to achieve 105 efficacy evaluable patients.

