10.5. Interim Analysis

There are no planned interim analyses for this study. Efficacy data generated in the MIRV program in patients with FR α high expression (by the PS2+ scoring method), includes a 44% Investigator-assessed ORR in the 27 patients in IMGN853-0401 and a 38% Investigator-assessed ORR in the 116 patients in IMGN853-0403 (Moore 2019). In addition, an analysis of patients derived from both Study 0401 and Study 0403 who are eligible for this study (n=70), revealed an ORR by investigator of 31.4% with a DOR of 7.8 months. Thus, an interim analysis for futility in the current study in the same or a very similar population is not warranted.

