2.2.2. Power and Sample Size

The primary endpoint of this study is ORR as assessed by the investigator. The study is designed to test the null hypothesis that the ORR is 12% (Eisenhauer 2009, Pujade-Lauraine 2014). The ORR will be estimated using the efficacy evaluable population as defined in Section 3.12.3.

Approximately 110 patients will be enrolled so that a total of 105 patients will be efficacy evaluable. A sample size of 105 efficacy evaluable patients achieves 90% power to detect a difference in ORR of 12% (24% vs 12%) using a one-sided binomial test. The target significance level (one-sided α level) is 0.025. The actual significance level achieved by this test is 0.0242. These results assume that the ORR is 12% under the null hypothesis and 24% under the alternative hypothesis.

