5.3.2. Additional Secondary Efficacy Analyses

The following additional efficacy endpoints will be summarized.

- PFS
- OS
- TTR
- GCIG CA-125 response

PFS and OS will be summarized using the Efficacy Evaluable population. Their distribution will be estimated using the Kaplan-Meier method. PFS and OS rates will be reported at 3-month intervals (eg, 3 months, 6 months, etc.). Median PFS and OS will be estimated the 50th percentile of the corresponding Kaplan-Meier estimates. The 95% CI for the 3-month intervals and median

times will also be provided. Additionally, the restricted mean survival time (RMST) will also be reported at 3-month intervals (eg, 3 months, 6 months, etc.).

The median follow-up time and its 95% CI will be estimated using reverse Kaplan-Meier method on OS.

GCIG CA-125 response rate will be calculated using the CA-125 Response-Evaluable population and its 95% exact CI will be estimated using the Clopper-Pearson method.

TTR will be summarized in patients with a confirmed BOR of CR or PR only with the simple summary statistics.

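### The scan interval doubles at Week 36, so the 9- and 12-month Kaplan-Meier rates for duration of response (DOR) tend to be too high, and no planned analysis shows by how much

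*SAP*

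**What the plan says.** - **Scan schedule.** Protocol 4.1.1 and 7.13.1 set scans every 6 (±1) weeks "from C1D1 for the first 36 weeks then every 12 weeks" (±3). The clock runs from first dose, not from response.
- **Dating of progression.** Table 3 in SAP 5.1.2 gives the PFS event date as "Date of first radiological assessment indicating progression (ie, OR = PD". The DOR text in SAP 5.1.1.2 says only that DOR ends at the date of PD or death. I take the same dating to apply there.
- **Events not dated at a scan.** Under SAP 5.1.1.2 a death keeps its own date. PD or death after a gap of 105 days or more is censored at the earlier scan.
- **Start of DOR.** The clock starts at the first scan showing response, not the confirmatory scan (SAP 5.1.1.2).
- **Estimates.** SAP 5.3.1 plans a Kaplan-Meier median with 95% CI, and "DOR rates will be reported at 3-month intervals (eg, 3 months, 6 months, etc". SAP 5.3.2 does the same for PFS and OS: "PFS and OS rates will be reported at 3-month intervals (eg, 3 months, 6 months, etc".
- **Sensitivity analysis.** SAP 5.5 repeats ORR, DOR and PFS by central review with the same methods. No interval-censored or midpoint analysis is planned.
- **Testing and expectation.** SAP 3.11.2 plans no test of any secondary endpoint. No expected DOR is given for this trial. The protocol's program figures are 7.8 months in 70 patients eligible for this study (Protocol 10.5: "revealed an ORR by investigator of 31.4% with a DOR of 7.8 months"), 7.8 and 5.8 months in two Phase 1 groups (1.6.1), and 5.7 months by central review in the prior Phase 3 study (1.6.2).

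**The concern.** A progression is seen only at a scan, so Kaplan-Meier on scan dates places it late. Before Week 36 the delay averages about half of 6 weeks, and afterwards about half of 12. The 9- and 12-month DOR landmarks fall after Week 36 for every responder, because 9 months is already 39 weeks from the response scan. Those rates therefore partly reflect the scan calendar, even if every scan is done on time.

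DOR is the key secondary endpoint of a single-arm trial, so its readers will compare it with outside figures such as the 4 to 8 months for single-agent chemotherapy in Protocol 1.3. The planned confidence intervals describe sampling error and do not show this shift. The central-review analysis repeats it.

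**Working it through.** **1. The plan's own figure.** The documents give no precision or expected value for DOR. Their only design figure is the ORR test: n = 105, 12% against 24%, one-sided 0.025. The smallest rejecting count is 20 responders, with exact level 0.0242 (as stated) and power 90.6%, consistent with the SAP's 90% and the protocol's 91%. At the program ORR of 31.4%, 0.314 × 105 ≈ 33 responders would enter the DOR analysis.

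**2. Which scan each DOR landmark reads.** One month = 30.4375/7 = 4.348 weeks, so 9 months = 39.1 weeks and 12 months = 52.2 weeks. Nominal scans fall at Weeks 6, 12, …, 36, 48, 60, 72.

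| First response | Landmark | Study week | Last scan, planned | Lag (weeks) | Last scan if 6-weekly | Lag (weeks) |
|---|---|---|---|---|---|---|
| Week 6 | 9 mo | 45.1 | 36 | 9.1 | 42 | 3.1 |
| Week 6 | 12 mo | 58.2 | 48 | 10.2 | 54 | 4.2 |
| Week 12 | 9 mo | 51.1 | 48 | 3.1 | 48 | 3.1 |
| Week 12 | 12 mo | 64.2 | 60 | 4.2 | 60 | 4.2 |

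For a Week-6 responder, the 9-month status is her status at (36 − 6)/4.348 = 6.9 months, and the 12-month status is that at (48 − 6)/4.348 = 9.7 months. Week-18 responders have the Week-6 lags. Week-12 and Week-24 responders lose nothing extra from the doubling.

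**3. PFS.** From first dose, months 3, 6, 9 and 12 are Weeks 13.0, 26.1, 39.1 and 52.2. The last scans are Weeks 12, 24, 36 and 48 on either calendar, so the lags (1.0, 2.1, 3.1 and 4.2 weeks) are identical. The program's median PFS of 4.8 and 6.7 months (Weeks 20.9 and 29.1) also falls before Week 36.

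**4. Where the median would fall.** A DOR of 7.8 months is 33.9 weeks. From response at Week 6 or 12 it ends at Week 39.9 or 45.9, inside the first 12-week gap. A DOR of 5.7 months (24.8 weeks) ends at Week 30.8 or 36.8, before or at the change.

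**5. Simulated size.** These assumptions are mine, not the documents': true onset uniform over Weeks 1 to 16; underlying median DOR 5.7 or 7.8 months; Weibull shape 1 or 1.5; scan dates uniform within the visit windows; response confirmed at the next scan; no deaths or censoring. Confirmation selects longer responses, so true values among confirmed responders exceed the underlying medians.

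| Median, shape | Measure | Planned KM | KM if 6-weekly | Response scan to true PD | True onset to true PD | Midpoint at both ends |
|---|---|---|---|---|---|---|
| 5.7, 1 | 9-mo % | 47.6 | 43.1 | 39.5 | 43.0 | 43.2 |
| | 12-mo % | 33.2 | 30.7 | 27.4 | 29.9 | 29.2 |
| | median, mo | 8.55 | 8.04 | 7.03 | 7.75 | 7.73 |
| 5.7, 1.5 | 9-mo % | 35.4 | 29.8 | 24.7 | 29.1 | 29.7 |
| | 12-mo % | 17.4 | 15.2 | 11.4 | 13.8 | 13.2 |
| | median, mo | 6.98 | 6.76 | 5.78 | 6.49 | 6.56 |
| 7.8, 1 | 9-mo % | 58.0 | 54.2 | 50.5 | 53.8 | 54.0 |
| | 12-mo % | 44.5 | 42.3 | 38.7 | 41.2 | 40.4 |
| | median, mo | 10.43 | 9.74 | 9.11 | 9.83 | 9.80 |
| 7.8, 1.5 | 9-mo % | 52.4 | 46.6 | 42.0 | 46.6 | 46.9 |
| | 12-mo % | 33.6 | 30.6 | 26.0 | 29.2 | 28.3 |
| | median, mo | 9.35 | 8.36 | 7.79 | 8.51 | 8.79 |

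- Planned KM minus documented response to true PD: about 6 to 11 points for the rates, 1.2 to 1.6 months for the median.
- Planned KM minus true onset to true PD: about 3 to 6 points, 0.5 to 0.9 months.
- 6-weekly KM minus true onset to true PD: about 1 point or less, −0.2 to +0.3 months.

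**6. Other response-time mixes.** Three other mixes of response timing, twelve scenarios in all, gave wider ranges. Against documented response the excess was 7.7 to 13.0 points at 9 months and 6.1 to 8.9 at 12. Against true onset it was 4.4 to 8.4 and 3.5 to 5.5. The part of the median shift due to the doubling was 0.04 to 1.1 months. In one case with scans exactly on schedule, the median was slightly low (9.66 against 9.87 months).

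**The case against.** - **The plan defines DOR between documented assessments.** Scan-dated Kaplan-Meier estimates that quantity. It is a stated convention, not a contradiction. This stands, but the estimate still depends on a calendar that changes partway, and nothing planned shows the dependence.
- **Response is also dated late, by about 3 weeks.** This stands and removes roughly half of the excess. Correcting only the progression end would over-correct: in the table, response scan to true PD is about 2 to 5 points and 0.7 months below true onset to true PD.
- **The shift is small beside sampling error.** With 33 responders the simulated standard deviation is about 1.7 to 2.0 months for the median and 8 to 9 points for the rates. This stands as to size. The shift is systematic, however, and the confidence intervals do not contain it.
- **The 105-day rule was left out of the table.** With scan dates uniform in the windows, 6 to 11% of progressions would meet it. Applying it in 7.8-month scenarios moved the 9-month rate by −0.3 to +0.7 points and the 12-month rate by 0 to +1.4, so it does not remove the excess.
- **Outside figures may be scan-dated too.** True, but the documents do not give those studies' scan schedules, so the delays cannot be assumed to match.

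**Conclusion.** The 9- and 12-month DOR rates tend to be too high. Under the stated assumptions the excess is about 6 to 11 points against progression measured from documented response, and about 3 to 6 points against true onset to true progression. Less even response timing can raise these figures somewhat. The effect on the median ranges from small to about 1.5 months, depending on the schedule and the true DOR. All sizes rest on assumed distributions without deaths.

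A reader might infer more, and the documents do not support it:

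- **That the median is inflated by construction because it is expected just after Week 36.** No expected DOR is stated, and the program values include 5.7 and 5.8 as well as 7.8 months. The late response date offsets part of the shift.
- **That every progression is scan-dated.** Deaths keep their date, and PD after a long gap is censored.
- **That PFS shares the problem.** At months 3 to 12 its rates read the same scans on either calendar.
- **That the trial's decision is affected.** The only test is on ORR.

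This is a cheap improvement to how durability is reported, not a flaw in the primary analysis.

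**What to change.** In SAP 5.5 add one DOR sensitivity analysis, for Investigator and central-review assessments:

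- Place each progression between the last scan without PD and the scan showing PD. Keep deaths at their exact date.
- Report it in two versions: (a) from the documented response date; (b) with response onset also interval-censored between the last scan without response and the first scan with it. For (b), use a doubly interval-censored estimate, or midpoints at both ends.
- Show its median and 3-monthly rates beside the Kaplan-Meier results. Add a table note that scan spacing changes from 6 to 12 weeks at Week 36.

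Both versions are feasible at this trial's size. For (a), over 400 simulated sets of 33 responders (underlying median 7.8 months, shape 1), a Turnbull estimate moved the mean 9-month rate from 58.6% to 51.5% (latent value 50.3%) and the median from 10.7 to 9.1 months (latent 9.2). For (b), the midpoint version in the table is within about 1 point and 0.3 months of the true values. If 80% of onsets fell before Week 6, it was off by up to about 2 points and 0.6 months, so the doubly interval-censored form is preferable.

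The cost is SAP wording and one extra analysis of dates already collected. SAP 1.1 allows changes before final database lock. The downside is a second, usually somewhat lower, set of late DOR rates to explain. No change to the scan schedule or the primary analysis is needed.

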5.3.2. Additional Secondary Efficacy Analyses

The following additional efficacy endpoints will be summarized.

- PFS
- OS
- TTR
- GCIG CA-125 response

PFS and OS will be summarized using the Efficacy Evaluable population. Their distribution will be estimated using the Kaplan-Meier method. PFS and OS rates will be reported at 3-month intervals (eg, 3 months, 6 months, etc.). Median PFS and OS will be estimated the 50th percentile of the corresponding Kaplan-Meier estimates. The 95% CI for the 3-month intervals and median

times will also be provided. Additionally, the restricted mean survival time (RMST) will also be reported at 3-month intervals (eg, 3 months, 6 months, etc.).

The median follow-up time and its 95% CI will be estimated using reverse Kaplan-Meier method on OS.

GCIG CA-125 response rate will be calculated using the CA-125 Response-Evaluable population and its 95% exact CI will be estimated using the Clopper-Pearson method.

TTR will be summarized in patients with a confirmed BOR of CR or PR only with the simple summary statistics.

5.4. Efficacy Analysis on Subgroups of Patients

Efficacy endpoints (ORR, DOR, PFS, OS, and GCIG CA-125 response rate) will be analyzed with the following subgroups of patients:

- Number of prior lines of therapy (1 vs 2 vs 3)
- Prior exposure to PARPi (yes vs no vs uncertain)
 - If patient participated in a double-blind randomized trial comparing PARP inhibitor to placebo and the actual treatment was unknown, patient will be summarized under 'uncertain' category.
- ADA status

The summaries for ORR and GCIG CA-125 response include the response rate and its 95% exact CI.

The summaries for time to event variables (DOR, PFS, and OS) include the number and percentage of events, median and its 95% CI.

5.5. Additional Sensitivity Analyses

Analysis of ORR, DOR, and PFS as assessed by BICR will be performed as sensitivity analysis using the same methods described in the previous sections.

5.6. Other Efficacy-related Summaries

Listings of efficacy-related data for will include the following:

- All lesion assessments (target lesion, non-target lesion, new lesion)
- New anti-cancer therapy
- Investigator's RECIST assessments
- CA-125 results
- Derived parameters for CA-125 response, BOR, PFS, DOR, and OS
- Censoring for time-to-event variables

6. SAFETY ANALYSES

The main safety summary tables will use data from the Safety population. Listings will be provided for patients in the Safety population.

6.1. Exposure

Summary tables will be provided with the following information.

Exposure to MIRV will be summarized with descriptive statistics for the number of doses received, the number of cycles received, duration of dosing (weeks), total cumulative dose (mg), absolute dose intensity (mg/kg/dose, calculated as total cumulative dose [mg])/number of valid drug administration records /AIBW [kg]).

The number of infusions with dose decreased, and dose delayed will also be summarized.

A listing will be provided with the information from all MIRV administration case report forms (CRFs) over the treatment period.

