5.2.2. Patient Assignment to Dosing Regimens

All patients will receive MIRV 6 mg/kg AIBW Q3W.

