5.5.2.2. Management and Dose Modification Guidelines

If a patient develops ocular symptoms of any grade, the patient is required to have a complete examination by an ophthalmologist. If a patient develops \geq CTCAE Grade 2 ocular symptoms, treatment with MIRV must be interrupted. Treatment should not be interrupted solely for Grade 2 ocular signs (eg, Grade 2 keratopathy) unless they are also associated with Grade 2 ocular symptoms. Treatment with MIRV may resume if ocular symptoms improve to Grade 1 or baseline within 28 days of the next scheduled MIRV dose (refer to [Table 5](#) for details). If ocular

symptoms last longer than 28 days, resumption of MIRV, with or without dose reduction, may be considered for those patients who have experienced clinical benefit if agreed upon between the Sponsor and the Investigator. Subsequent eye examinations will be scheduled to occur in every other cycle going forward, from the time that the AE was initially reported, and at either the EOT visit or 30-Day Follow-up Visit after treatment discontinuation, even if the results of the patient’s ocular exam shows no obvious clinical findings. Management of treatment-emergent ocular AEs with inflammatory characteristics should include corticosteroid eye drops and/or other measures as indicated by an ophthalmologist.

Table 5: Management of Ocular Symptoms

Severity Grade (CTCAE v5.0)	Management	Guidelines for MIRV Dose Modifications
Grade 1	Complete eye exam as outlined in Schedule of Assessments (Table 2) Monitor for worsening symptoms	Continue MIRV dosing
Grade 2	Complete eye exam as outlined in Schedule of Assessments (Table 2) Repeat complete exam as clinically indicated Patients should have weekly symptomatic ocular assessments by the Investigator until the symptoms resolve to Grade 1 or baseline or are deemed to be irreversible by the Investigator	Hold MIRV dosing until AE has resolved to Grade 1 or better Patients with ocular symptoms lasting < 14 days may be allowed to resume MIRV at the same dose level Patients with ocular symptoms lasting ≥ 14 days but no more than 28 days may resume MIRV at one lower dose level Recurrence of Grade 2 toxicity on subsequent cycles despite best supportive care will require a MIRV dose reduction of one dose level

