Grade 3	Complete eye exam as outlined in Schedule of Assessments (Table 2). Repeat complete exam as clinically indicated Patients should have weekly symptomatic ocular assessments by the Investigator until the symptoms resolve to Grade 1 or baseline or are deemed to be irreversible by the Investigator	Hold MIRV dosing Patients may be allowed to resume MIRV at a lower dose after AE has resolved to Grade 1 or better within 28 days Recurrence of Grade 3 toxicity on subsequent cycles despite best supportive care will require a MIRV dose reduction of one dose level
Grade 4	Complete eye exam as outlined in Schedule of Assessments (Table 2). Repeat complete exam as clinically indicated Patients should have weekly symptomatic ocular assessments by the Investigator until	Permanently discontinue MIRV

Severity Grade (CTCAE v5.0)	Management	Guidelines for MIRV Dose Modifications
	the symptoms resolve to Grade 1 or baseline or are deemed irreversible by the Investigator	

Abbreviations: AE = adverse event; CTCAE = common terminology criteria for adverse events; MIRV = mirvetuximab soravtansine.

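### The SAP's absolute dose intensity is a mean dose per infusion with no time term, so no exposure summary shows the dose rate delivered against the planned every-3-week regimen

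*SAP*

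**What the plan says.** SAP 6.1 (Exposure) lists the exposure summaries: number of doses, number of cycles, duration of dosing in weeks, total cumulative dose in mg, and "absolute dose intensity (mg/kg/dose, calculated as total cumulative dose [mg])/number of valid drug administration records", with a further division by AIBW in kg. It adds counts of infusions that were decreased or delayed, and a listing of every administration form. The SAP defines no intensity per unit of time and no intensity relative to plan.

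The regimen itself is a dose and an interval. Protocol 5.2.2: "All patients will receive MIRV 6 mg/kg AIBW Q3W".

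Protocol 5.5.2.2 and Table 5 govern holds for ocular symptoms:

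- At Grade 2 or above, "treatment with MIRV must be interrupted".
- For Grade 2, the instruction is "Hold MIRV dosing until AE has resolved to Grade 1 or better".
- Short Grade 2 episodes carry no reduction: "Patients with ocular symptoms lasting < 14 days may be allowed to resume MIRV at the same dose level".
- Patients with Grade 2 symptoms of 14 to 28 days "may resume MIRV at one lower dose level".
- For Grade 3: "Patients may be allowed to resume MIRV at a lower dose after AE has resolved to Grade 1 or better within 28 days".

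Holds resumed at the same dose also occur outside the eye. Table 3 allows this for Grade 2 and 3 neutropenia, and for Grade 2 and 3 thrombocytopenia without the bleeding exception.

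**The concern.** Dose intensity is commonly read as drug delivered per unit of time. The SAP quantity is drug delivered per infusion. A hold postpones or removes an infusion, so the numerator and the denominator stay in step and the ratio does not fall.

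The regimen is planned every 3 weeks and the protocol requires holds for several toxicities, some of them without a reduction. How far patients with toxicity fall below the planned rate is therefore a natural tolerability question, and the line called dose intensity does not answer it. Exposure also matters to the programme's own reasoning: Protocol 5.5.2.1 reports that plasma exposure was related both to ocular events and to response.

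**Working it through.** The documents state no numerical dose intensity, so there is no figure to reproduce. The check applies the SAP formula and a time-based formula to the same illustrative patients.

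**Inputs**
- Planned dose 6 mg/kg AIBW every 3 weeks (Protocol 5.2.2), so 6/3 = 2.0 mg/kg/week.
- First reduced level 5.0 mg/kg AIBW (Protocol Table 4).
- Ocular rules for holding and resuming (Protocol 5.5.2.2, Table 5).
- Assumptions: six doses per patient; one constant AIBW, which then cancels; each hold delays the next dose by its stated length; only doses given are valid records; 3 weeks are credited after the last dose.

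**Formulas**
- SAP measure = sum of doses in mg/kg ÷ number of doses.
- Weekly rate = sum of doses in mg/kg ÷ (weeks from first to last dose + 3).
- Relative intensity = weekly rate ÷ 2.0.

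**Results**

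| Path, six doses | Weeks | SAP measure | Weekly rate | Relative |
|---|---|---|---|---|
| No hold, all at 6 | 15 + 3 = 18 | 36/6 = 6.00 | 36/18 = 2.00 | 100% |
| One 13-day hold, all at 6 | 18 + 13/7 = 19.86 | 6.00 | 36/19.86 = 1.81 | 91% |
| Two 21-day haematological holds, all at 6 | 18 + 6 = 24 | 6.00 | 36/24 = 1.50 | 75% |
| Reduced to 5 from dose 3, no hold | 18 | 32/6 = 5.33 | 32/18 = 1.78 | 89% |
| 14-day hold before dose 3, then 5 | 18 + 2 = 20 | 5.33 | 32/20 = 1.60 | 80% |
| 28-day hold before dose 3, then 5 | 18 + 4 = 22 | 5.33 | 32/22 = 1.45 | 73% |

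Rows 1 to 3 share one SAP value while the delivered rate runs from 100% to 75% of plan. Rows 4 to 6 share another (5.33, which is 89% of 6) while the rate runs from 89% to 73%. Row 4 is a comparator that isolates the reduction. Row 3 sits at the 21-day retreatment limit in the footnote to Table 3.

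**Dependence on the definition of a valid record.** The SAP does not define the term. If a skipped dose were kept as a valid record of 0 mg, six full doses plus one such record would give 36/7 = 5.14, and the measure would respond to skipped doses. The plain reading is that it counts doses given.

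**The case against.** The strongest reply has three parts.

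**The number is right for what it says.** The unit, mg/kg/dose, stands beside the term, and cumulative dose and number of doses are reported directly. This stands. A reader might infer that delivered exposure is overstated. The documents do not support that: no delivered quantity is misstated, and the SAP reports no percentage of plan. The fault is a label that suggests a rate.

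**Delays are not hidden.** SAP 6.1 gives duration in weeks, infusions delayed and the administration listing. SAP 6.2 tabulates treatment-emergent adverse events leading to delay and to reduction, overall and for the ocular, neuropathy and pneumonitis groups. This also stands, so it would be too strong to say that tolerability of the regimen cannot be read from the outputs. These summaries still leave one gap. Counts of delayed infusions carry no length of delay. Separate summaries of weeks and cumulative mg cannot be combined into a patient-level rate, the more so because cumulative dose is in mg rather than mg/kg. The listing holds the dates, but it leaves the derivation to the reader.

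**Long holds usually bring a reduction, which does move the measure.** A reader might picture six full doses with two 4-week ocular holds: 36/26 = 1.38 mg/kg/week, 69% of plan, against an SAP value of 6.00. Table 5 does not make that a routine path. Symptoms of 14 to 28 days, recurrent Grade 2 and Grade 3 all lead to a lower level; full-dose resumption after more than 28 days needs clinical benefit and agreement between sponsor and investigator. With reductions after each hold (6, 6, 5, 5, 4, 4) the SAP value is 30/6 = 5.0, 83% of 6, against 30/26 = 1.15 mg/kg/week, 58% of plan. The measure moves, but by less than the rate.

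Nor do the documents support calling holds the main tool for ocular toxicity. Holding is mandatory at Grades 2 and 3, but the protocol also mandates corticosteroid and lubricating drops (5.4.2) and uses dose reductions.

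**Conclusion.** The point holds as a matter of labelling and of one missing summary. What SAP 6.1 calls absolute dose intensity is a mean dose per infusion; it is unchanged by a hold resumed at the same dose and reflects a longer hold only through any reduction that follows. On the two ocular illustrations the gap is 100% against 91%, and 89% against 73%, taking the SAP value as a share of 6 mg/kg.

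These figures illustrate possible patients and do not forecast the trial's average, which depends on how often and how long dosing is held. They rest on the assumptions listed with the inputs, chiefly that valid records are doses given. Table 5 measures how long symptoms last, so an episode that begins between doses would delay dosing by less than the stated hold.

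The consequence is confined to a descriptive safety summary. No hypothesis test, endpoint or analysis population is affected, and the objective response rate analysis is untouched. This is a worthwhile small improvement, not a flaw in the trial's conclusions.

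**What to change.** In SAP 6.1:

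1. Add dose intensity per 3 weeks = cumulative mg ÷ AIBW ÷ (weeks from first to last dose + 3) × 3. The two ocular illustrations become 36/19.86 × 3 = 5.44 and 32/22 × 3 = 4.36 mg/kg per 3 weeks.
2. Add relative dose intensity = that value ÷ 6 mg/kg, the planned dose per 3 weeks.
3. Keep the present quantity, relabelled as mean dose per infusion.
4. State that valid administration records are doses actually given.

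The cost is two derived variables from data already collected, and a reported intensity that will be lower than the present one wherever doses were delayed. One limit should be noted with the table: crediting 3 weeks after the last dose means that a hold ending in discontinuation, with no further dose, does not lower the new measure either. The discontinuation tables cover those patients. No dosing rule changes.
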